1.3.3.9 Tumor Lysis Syndrome

There have been reports of tumor lysis syndrome (TLS) events in subjects treated with single-agent ibrutinib or in combination with chemotherapy. Subjects at risk of tumor lysis syndrome are those with comorbidities and/or risk factors such as high tumor burden prior to treatment, increased uric acid (hyperuricemia), elevated lactate dehydrogenase (LDH), bulky disease at baseline, and pre-existing kidney abnormalities.

1.4 Study rationale

It is becoming increasingly clear that the microenvironment has a crucial role in the progression of both hematological and solid tumors. In particular, preclinical data suggests that mast cells are recruited within NETs where they remodel the stroma and stimulate angiogenesis, driving macroscopic tumor expansion¹⁶. Inhibitors of mast cell degranulation have been shown to block this process, driving tumor shrinkage, at least in mouse models²². Ibrutinib can affect mast cell degranulation, acting downstream the high affinity IgE receptor FcεRI¹⁹. Given its favorable risk/benefit ratio for investigation in NETs, we plan to test the hypothesis whether ibrutinib can cause tumor regression in both carcinoid tumors and pNETs.

2. Study objectives

The primary purpose of the study is to determine the objective response rate to ibrutinib therapy in patients with advanced (unresectable or metastatic) low to intermediate grade carcinoid tumors or pNETs.

Secondary objectives are:

- to investigate the progression-free survival (PFS) and overall survival (OS) associated with ibrutinib in patients with advanced carcinoid tumors or pNETs;
- to evaluate the duration of response of carcinoid or pNET patients receiving ibrutinib;
- to assess changes in tumor markers and changes in quality of life (QOL) in NET patients administered with ibrutinib;
- to determine the safety and tolerability of ibrutinib in this patient population.

2.1 Selection of doses

Based on the tolerable side-effect profile of ibrutinib at doses of 560 mg daily in other neoplasms and pharmacokinetic data demonstrating therapeutic drug levels at that level (see section 1.3.2), the dose of ibrutinib in this study will be 560 mg once daily. If tolerability issues occur, the treatment dose may be reduced as described in section 5.2.

3. Endpoints

3.1 Primary endpoints

1. Overall radiographic response rate (ORR), as defined by RECIST v1.1.

3.2 Secondary endpoints

1. Median PFS and PFS rate at 1 year
2. Median OS and OS at 1 year
3. Duration of response
4. Adverse events (AEs)

5. Changes in neuroendocrine tumor markers (such as chromogranin A or pancreatic polypeptide), or hormonal assays (such as urine 5-HIAA, gastrin, glucagon, vasoactive intestinal peptide, etc) if elevated at baseline (> upper limit of normal, ULN);
6. Changes in quality of life (as measured by EORTC questionnaires EORTC QLQ-C30 and QLQ GI-NET21).

3.3 Exploratory endpoint

1. To determine whether the presence and activation of mast cells in the tumor tissue sample predicts for response;
2. To determine whether changes in serum Tryptase-β2 correlate with response.

4. Investigational plan

4.1 Overall study design

This is a prospective phase II open-label trial, stratifying patients equally into two cohorts consisting of carcinoid tumors and pNETs.

4.2 Treatment

The investigational drug used in this study is ibrutinib 560 mg. Ibrutinib will be administered orally once daily and each cycle will be defined as 4 weeks duration. Study treatment should begin within 14 days following enrollment into the study and continue until disease progression, unacceptable toxicity, or withdrawal of consent. Safety and efficacy will be assessed throughout the treatment period.

4.3 Study population

The study population will consist of adult patients with histologically confirmed low to intermediate grade NETs of the GI tract, lungs and unknown primary (carcinoid tumors) or pNETs. All patients must be confirmed to have advanced disease. The study will enroll up to 51 patients in two cohorts (30 carcinoid and 21 pNET patients).

4.4 Inclusion/exclusion criteria

The investigator or his/her designee must ensure that all patients who are offered enrollment in the study meet all of the following inclusion and exclusion criteria:

4.4.1 Inclusion criteria

1. Locally unresectable or metastatic carcinoid or pNET;
2. Measureable disease by RECIST criteria;
3. Tumors must be histologically or cytologically proven and considered low or intermediate grade. Patients with high grade neuroendocrine carcinomas or small cell carcinomas are excluded from the study;
4. Evidence of progressive disease within 12 months of study entry;
5. Allowed prior therapies include:

- a) Surgery (major surgery at least more than four weeks prior to baseline assessment);
 - b) Locoregional therapy such as: chemoembolization, radio-embolization, radiofrequency ablation, radiotherapy as long as there is progressive measurable disease outside the area of locoregional therapy or there is progression in the previously treated areas;
 - c) Any number of previous lines of systemic therapy. Last treatment before enrollment must have occurred more than 4 weeks for chemotherapy, 6 weeks for antibodies or more than 5 half lives of prior TKIs or small molecules;
6. Prior or concurrent therapy with somatostatin analogs is permitted for patients with secretory NET;
 7. All patients with gastroenteropancreatic NETs must have progressed on (or are intolerant of) prior somatostatin analog;
 8. Patients with pancreatic NETs must have progressed on (or are intolerant of) either everolimus or sunitinib;
 9. Age \geq 18 years;
 10. ECOG performance status of 0-2;
 11. Life expectancy 12 weeks or more;
 12. Adequate bone marrow function as shown by: absolute neutrophil count \geq 1,000/mm³, Platelets \geq 100,000/mm³, Hb > 10 g/dl;
 13. Adequate liver function as shown by: serum bilirubin \leq 1.5 x ULN, and serum transaminases activity \leq 2.5 x ULN, with the exception of serum transaminases ($< 3 \times$ ULN) if the patient has liver metastases;
 14. Adequate renal function as shown by serum creatinine \leq 2 mg/dl;
 15. Women of childbearing potential must have a negative serum pregnancy test within 7 days of the administration of the first study treatment. Women must not be lactating. Both men and women of childbearing potential must be advised of the importance of using effective birth control measures during the course of the study. Childbearing potential for women and men is defined in section 4.4.3;
 16. Signed informed consent to participate in the study must be obtained from patients after they have been fully informed of the nature and potential risks by the investigator (or his/her designee) with the aid of written information.

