6.1 Pretreatment Evaluation

Baseline tumor and patient characteristics including:

- Patient demographics: age, gender and race
- Medical history;
- Medications;
- ECOG performance status;
- Type of neuroendocrine tumor: primary site (if known) vs. unknown;
- Differentiation or grade (if available);
- Known sites of metastases;
- Presence or absence of hormonal syndrome (carcinoid syndrome, gastrinoma syndrome, insulinoma syndrome, etc.);
- Presence or absence of a pathologically elevated hormone or biomarker;
- EORTC QLQ C-30 and EORTC QLQ GI-NET21 questionnaires.

Tests to be performed within 28 ±2 days prior to initiation of therapy (if day 28 falls on a weekend or holiday the deadline may be extended to the next working day):

- Radiologic assessment of tumor burden by CT scan or MRI; In all cases, imaging studies should encompass the abdomen and any other known sites of measurable disease. For small bowel NETs, imaging of the abdomen and pelvis is recommended. For pancreatic NETs, abdominal imaging is sufficient if there are no known extra abdominal sites. For lung NETs, imaging of the thorax and abdomen is recommended.
- Assessment of secretory proteins. All patients will undergo an initial assessment of chromogranin A. Patients with suspected serotonin-producing tumors (and all patients with midgut carcinoid tumors) will have a 24 hour urine 5-HIAA measured at baseline. Other possible neuroendocrine tumor markers/hormones (e.g. pancreatic polypeptide,

gastrin, glucagon, etc.) may be collected at the discretion of the investigator based on clinical symptoms and tumor location.

Tests to be performed within 14 ±2 days prior to initiation of therapy (if day 14 falls on a weekend or holiday the deadline may be extended to the next working day):

- History and physical evaluation including height, weight, vital signs and performance status;
- Baseline hematological and biochemical profiles including CBC with differential and comprehensive metabolic panel (fasting glucose, sodium, potassium, calcium, chloride, bicarbonate, creatinine, blood urea nitrogen, albumin, SGOT (AST) SGPT (ALT) total bilirubin and alkaline phosphatase);
- Serum pregnancy test for women of childbearing potential;
- Correlative laboratory studies with the potential to correlate with response to the treatment (measurement of serum Tryptase-β2).

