6.4 Evaluation schema

Table 6-5 lists all of the assessments and indicates the visits at which they are to be performed with an "X". All data obtained from these assessments must be supported in the patient's source documentation.

Table 6-5 Visit evaluation schedule

Evaluation	Screening/ Baseline ^a	Each Cycle (day 1 \pm 2)	Every 3 Cycles \pm 1 week (until disease progression, unacceptable toxicity or withdrawal of consent)	End ^b
Informed consent	X			
Demographics	X			
Relevant medical	X	X		X

history/ current medical conditions				
Diagnosis and extent of cancer	X			
Physical exam	X	X		X
Vital signs	X	X		X
ECG ^c	X			
ECOG Performance Status	X	X		X
CBC with differential ^d	X	X		X
Glycosylated hemoglobin	X			
Fasting Comprehensive metabolic panel ^e	X	X		X
Pregnancy test and review of contraception ^f	X			
Secretory hormones ^g and serum chromogranin A	X		X	X
Radiologic assessment of tumor burden ^h	X		X	X
Adverse events ⁱ	X	X		X
Concomitant medications ^j	X	X		X
EORTC QLQ C-30 and EORTC QLQ GI-NET21 questionnaires	X		X	
Correlative laboratory studies ^k	X		X	

^a Screening includes review of: demography/informed consent, inclusion/exclusion criteria, relevant medical history/concomitant medications, diagnosis and extent of cancer.

^b Patients who interrupt or permanently discontinue ibrutinib due to an adverse event or abnormal laboratory value must be followed at no less than monthly intervals, until resolution of toxicity to less than grade 2. These patients will be censored, and tumor assessment will be performed off trial at treating physician's discretion.. Patients will be followed for OS each 12 months using their charts or the Social Security Death Index.

^c ECG should be done at any time when clinically indicated.

^d Complete blood count must include: hemoglobin, hematocrit, platelets, total white blood cell count and differential.

^e Comprehensive metabolic panel should include fasting glucose, sodium, potassium, calcium, chloride, bicarbonate, creatinine, blood urea nitrogen, albumin, total protein, SGOT (AST), SGPT (ALT), total bilirubin and alkaline phosphatase.

^f For women of child-bearing potential: women of childbearing potential must have a negative serum pregnancy test within 14 days of enrollment. Acceptable contraception must be used while on study and for at least 60 days after last dose of ibrutinib.

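### Section 6.1 and Table 6-5 allow an older pregnancy test than the 7-day limit in inclusion criterion 15, and nothing in the schedule enforces that limit

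*Combined protocol and SAP*

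**What the plan says.** The protocol states the timing of one safety test in three places.

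- **Section 4.4.1, criterion 15:** women of childbearing potential "must have a negative serum pregnancy test within 7 days of the administration of the first study treatment". Section 4.4 makes this binding: the investigator must ensure that patients offered enrollment "meet all of the following inclusion and exclusion criteria".
- **Section 6.1:** under the line "Tests to be performed within 14 ±2 days prior to initiation of therapy" the list includes "Serum pregnancy test for women of childbearing potential".
- **Section 6.4, Table 6-5 footnote f:** "women of childbearing potential must have a negative serum pregnancy test within 14 days of enrollment".

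Three further provisions decide how these work together. The table row "Pregnancy test and review of contraception" is marked only in the Screening/Baseline column. Footnote a places the eligibility check there too: "Screening includes review of: demography/informed consent, inclusion/exclusion criteria". Sections 4.2 and 5.1 have treatment starting up to 14 days after enrollment.

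**The concern.** The three windows differ in length (7, 14 ±2 and 14 days) and in anchor: two count from the first dose and one from enrollment. Sites usually work from the visit table and the list of pretreatment tests. Here both are looser than the eligibility rule, and neither refers back to it.

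The anchor adds a second difficulty. Eligibility is reviewed at screening, but criterion 15 depends on the date of first dose, which may fall two weeks after enrollment. Compliance therefore cannot always be confirmed when eligibility is signed off.

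What is at stake is patient safety. Section 1.3.1.3 reports increased post-implantation loss and visceral malformations in reproductive studies of ibrutinib, at about 14 times the AUC of patients on 560 mg daily. A woman dosed on an out-of-window test would also be an eligibility deviation that the schedule itself invited.

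**Working it through.** The protocol gives no figure of its own to reproduce. The check converts each rule to the longest interval it permits between test and first dose.

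**Notation, in whole days.** *g* is the time from test to first dose. *L* is the time from enrollment to first dose, 0 to 14 (Sections 4.2 and 5.1).

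| Rule | Condition | Longest *g* | Excess over 7 days |
|---|---|---|---|
| Criterion 15 | *g* ≤ 7 | 7 | – |
| Section 6.1 | *g* ≤ 14 + 2 | 16 | 16 − 7 = 9 |
| Footnote f alone | test up to 14 days before enrollment, plus *L* ≤ 14 | 14 + 14 = 28 | 28 − 7 = 21 |
| Section 6.1 and footnote f together | both conditions | 16 | 9 |

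The last row is the realistic one for a site that follows the schedule and overlooks criterion 15, because Section 6.1 then caps the interval. Section 6.1 also moves the deadline to the next working day when day 14 is a weekend or holiday. Whether that lengthens or shortens the interval is unclear, so it is left out.

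**Do the rules conflict outright?** There are 15 values of *L* (0 to 14) and 8 values of *g* that meet criterion 15 (0 to 7), so 15 × 8 = 120 combinations. All have *g* ≤ 16, so all meet Section 6.1. The time from test to enrollment, *g* − *L*, runs from 0 − 14 = −14 to 7 − 0 = 7. All 120 therefore lie within 14 days of enrollment when footnote f is read as allowing a test on either side of it. On that reading the windows are nested, and one test can satisfy all three.

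**When is a screening test not enough?** A test done on or before the day of enrollment has *g* ≥ *L*. For *L* = 8 to 14, *g* is at least 8 and criterion 15 fails. That is 7 of the 15 permitted lags. On those lags the woman needs a test after enrollment, and neither Section 6.1 nor Table 6-5 asks for a repeat.

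**The case against.** The strongest reply is that nothing here is contradictory. Section 4.4 makes every criterion mandatory, so 7 days is the rule. No text authorises dosing on an older test, and a site can meet all three statements at once. The column is headed Screening/Baseline and Section 6.1 counts from the start of therapy, so a test after enrollment and before the first dose fits the schedule as written. The 28-day figure requires a site to ignore Section 6.1 as well as criterion 15. The count of 7 lags in 15 is a count of calendar days, not a frequency, because the documents give no distribution of the lag. Other protections exist as well: criterion 15 requires advice on birth control, and footnote f adds "Acceptable contraception must be used while on study and for at least 60 days after last dose of ibrutinib". The reported reproductive toxicity arose at far higher exposure than patients will have.

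Most of this stands and limits the size of the point. Criterion 15 governs, 16 days is the figure to use, and the 7-in-15 count must not be read as about half of patients. It does not remove the fault. A schedule that permits a late baseline test does not require one. The two places that tell staff when to test still state longer limits than the rule they are meant to carry out.

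**Conclusion.** The concern holds as an internal inconsistency with a patient-safety consequence. The binding limit is 7 days, while the schedule sections taken together allow 16, an excess of 9 days. Footnote f alone would allow 28, an excess of 21, but only if Section 6.1 is also disregarded. For lags of 8 to 14 days, a test done on or before enrollment cannot meet criterion 15.

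These figures assume whole days, the full use of the ±2 day allowance, and a first dose no later than 14 days after enrollment. The documents do not say how many women of childbearing potential will enroll or how long the lag will usually be, so the number who might be affected is unknown. The response-rate endpoint, power and type I error are not touched.

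**What to change.** 1. In Section 6.1, take the serum pregnancy test out of the 14 ±2 day list and give it its own line: within 7 days before the first dose of ibrutinib.
2. In Table 6-5 footnote f, replace the 14-day window from enrollment with the same wording.
3. Add one sentence to Table 6-5: if the screening test is more than 7 days old on the planned day of first dose, it is repeated and must be negative before dosing.

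The longest test-to-dose interval is then 7 days throughout. The change sets no new standard, since it only carries the protocol's existing criterion into the schedule. It costs edits in two places, one added sentence, and an occasional repeat blood test for a woman whose first dose comes more than 7 days after her screening test.

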4.4.2 Exclusion criteria

1. High grade NET or small cell neuroendocrine carcinoma;
2. Clinically apparent central nervous system metastases or carcinomatous meningitis;
3. Known positive test for human immunodeficiency virus (HIV), hepatitis B virus (HBV), or hepatitis C virus (HCV);
4. History of stroke or intracranial hemorrhage within 6 months prior to the first dose of study drug;
5. Clinically significant cardiovascular disease such as uncontrolled or symptomatic arrhythmias, congestive heart failure, or myocardial infarction within 6 months of screening, or any class III or IV cardiac disease as defined by the NYHA functional classification;
6. Requirement for anticoagulation with warfarin or similar vitamin K antagonists.

7. Requirement for treatment with a strong cytochrome P450 (CYP) 3A4/5 inhibitor. (See Appendix A)
8. Prior antitumor therapy within 2 weeks of enrollment (with the exception of somatostatin analogs);
9. No other active malignancy within 3 years of enrolment except adequately treated basal cell or squamous cell skin cancer, in situ cervical cancer, adequately treated stage I or II cancer from which the patient is currently in complete remission, or any other cancer from which the patient has been disease free for at least three years;
10. Any medical condition or organ system dysfunction which, in the investigator's opinion, could compromise the patient's safety, interfere with the absorption or metabolism of ibrutinib;
11. Known hypersensitivity to ibrutinib or any component of the ibrutinib formulation;
12. History of noncompliance to medical regimens or unwillingness to comply with the protocol.
13. Currently active, clinically significant hepatic impairment Child-Pugh class B or C according to the Child Pugh classification (see Appendix D)

Comment [AT2]: RESPONSE REQUIRED:

Please include the following exclusion criteria regarding hepatotoxicity.

4.4.3 Definition of childbearing potential

All women are considered of childbearing potential, unless they meet at least one of the following criteria:

a) Females who are menopausal, defined as follows: i) Females who are younger than 55 years old will be considered menopausal if they satisfy all the following three requirements during screening: 1) they are in amenorrhea, defined as absence of menstruation for the previous 12 months; 2) they have a negative urine pregnancy test; and 3) they have a serum FSH level within the laboratory reference range for postmenopausal females; ii) Females who are older than 55 years old: they will be considered menopausal if they are in amenorrhea, defined as absence of menstruation for the previous 12 months before screening.

b) Females who have a documented hysterectomy and/or bilateral oophorectomy and/or tubal ligations.

All men are considered of childbearing potential, unless they meet at least one of the following criteria:

a) Males who have a documented vasectomy more than 6 months prior to the administration of the first study treatment.
 b) Female partner/partners who are menopausal (as previously defined) and/or who have a documented hysterectomy and/or bilateral oophorectomy and/or tubal ligations.

5. Study Medication

5.1 Study drug: ibrutinib

The investigational drug used in this study is ibrutinib, available as 140 mg capsules. The inactive ingredients of ibrutinib include: microcrystalline cellulose, croscarmellose sodium, sodium lauryl sulfate and magnesium stearate.

Pharmacyclics will supply ibrutinib as long as the patient remains on study, shows continuous benefit from treatment, and there are no safety concerns. Ibrutinib should be stored at room temperature (20°C to 25°C, equivalent to 68°F to 77°F). Excursions are permitted between 15°C and 30°C (59°F to 86°F).

The starting dose is 560 mg (four 140 mg capsules) taken once daily orally. Doses should be taken approximately the same time each day, without scheduled breaks. Patients who vomit anytime after taking a dose should not “make it up” with extra doses, but instead resume subsequent doses as planned. Any missed dose may be taken as soon as possible on the same day with a return to the normal schedule the following day. If doses are missed or vomited, this must be indicated in the source documents and CRFs. A treatment cycle will be defined as 4 weeks duration. To monitor the correct self-administration of ibrutinib, enrolled patients will be provided with a diary.

Study treatment should begin within 14 days following enrollment onto the study. Patients should be requested to bring their unused medication to the clinic each visit. Compliance should be verified by the investigator's staff through counting the number of capsules consumed between visits. The investigator (or his/her designee) will document dosage administration and all dose changes during the study in the CRF. The dose, amount dispensed, amount received, and amount remaining unused must be recorded.

Patients will be assessed for response after every 3 cycles (12 weeks) of therapy. Patients with evidence of stable disease or response to therapy as defined by RECIST v1.1 will continue protocol therapy. The dose of ibrutinib will be adjusted for toxicity as outlined below. Patients with unacceptable toxicity or progressive disease will discontinue protocol therapy.

5.2 Dose Modification

Ibrutinib should be held or reduced in dose for toxicity or for concomitant use of CYP3A inhibitors (see Appendix A), as described in the sections below. Ibrutinib dosing adjustments are to be made according to the greatest degree of toxicity observed. Doses of ibrutinib which have been reduced for toxicity may not be re-escalated. All interruptions or changes to study drug administration must be recorded. If any patient discontinues study treatment or post-treatment observation, then the reason will be recorded.

Patients experiencing drug-related toxicities that are grade 1 or 2 according to CTCAE criteria should continue ibrutinib without dose modification. However the investigator may reduce the dose by one level if a grade 2 toxicity persists and significantly affects patient quality of life. If a patient experiences a CTCAE grade 3 or higher non-hematological toxicity, a grade 3 or higher neutropenia with infection or fever, or a grade 4 hematological event that is considered drug-related, ibrutinib should be held until resolution of toxicity to ≤ grade 1. Then the drug should be reinitiated at the starting dose. If the toxicity reoccurs, the dose should be reduced by one capsule (140 mg per day). A second reduction of dose by 140 mg may be considered as needed as per Table 5-2. If a patient experiences these drug-related toxicities despite two dose reductions, ibrutinib should be discontinued and the patient should be taken off the study. Patients should also be removed from study if off treatment for >3 weeks.

Recommended dose modifications for these toxicities are described below:

Table 5-2: Recommended dose modifications for ibrutinib

Toxicity occurrence	Dispensed As
First	Restart at 560 mg daily
Second	Restart at 420 mg daily
Third	Restart at 280 mg daily
Fourth	Discontinue Ibrutinib

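### For a patient already cut to 420 mg for grade 2 toxicity, Section 5.2 bars a return to 560 mg, yet its restart sentence and Table 5-2 prescribe one, and no precedence is stated

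*Combined protocol and SAP*

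**What the plan says.** Section 5.1 sets the dose: "The starting dose is 560 mg (four 140 mg capsules) taken once daily orally".

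Section 5.2 then gives these rules:

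- A ban, with no exception: "Doses of ibrutinib which have been reduced for toxicity may not be re-escalated".
- An optional cut below the severe range: "the investigator may reduce the dose by one level if a grade 2 toxicity persists" and clearly impairs quality of life.
- A restart rule after a qualifying event, which is a drug-related non-hematological toxicity of grade 3 or more, grade 3 or worse neutropenia with fever or infection, or a grade 4 hematological event. The drug is held until recovery to grade 1 or better. "Then the drug should be reinitiated at the starting dose".
- A rule for recurrence: "If the toxicity reoccurs, the dose should be reduced by one capsule (140 mg per day"). After that, "A second reduction of dose by 140 mg may be considered as needed as per Table 5-2".
- Discontinuation if such toxicity occurs despite two reductions.

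Table 5-2, introduced as recommended modifications for these toxicities, reads "Restart at 560 mg daily" at the first occurrence, "Restart at 420 mg daily" at the second, 280 mg at the third, and stop at the fourth.

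**The concern.** The restart sentence and the table are written for a patient who comes to the first severe event on the full dose. Section 5.2 itself creates another kind of patient: one already lowered to 420 mg because grade 2 toxicity would not settle. For that patient the restart instruction is an increase above a toxicity-reduced dose, which the ban forbids.

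The stake is dosing safety. An investigator who follows the restart sentence or the table returns a patient who did not tolerate 560 mg to that dose directly after a severe drug-related event. At a second event, an investigator who follows the table may leave a patient at 420 mg with no reduction at all. Two investigators could dose the same patient differently, each with a line of the protocol in support.

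**Working it through.** The plan states no figure to reproduce here. The check is to trace the rules patient by patient.

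**Inputs**

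- Starting dose: 4 × 140 = 560 mg (Section 5.1).
- One level: 140 mg. Section 5.2 does not define the word, but the one-capsule step and the 560, 420, 280 ladder in Table 5-2 fix it. So 560 − 140 = 420 mg and 420 − 140 = 280 mg.

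**Step 1: no earlier cut.** At the first event the patient is on 560 mg and restarts at 560 mg. That is not a re-escalation. At later events the text gives 560 − 140 = 420 mg and 420 − 140 = 280 mg, the same as rows two and three. There is no conflict.

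**Step 2: cut to 420 mg for grade 2 toxicity, then a first qualifying event.**

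| Rule | Restart dose |
|---|---|
| Restart sentence, Section 5.2 | 560 mg |
| Table 5-2, row one | 560 mg |
| Ban on re-escalation, Section 5.2 | at most 420 mg |

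Difference: 560 − 420 = 140 mg/day. Ratio: 560/420 = 1.33.

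**Step 3: a second qualifying event while on 420 mg.** The patient may be at 420 mg because the ban was respected at the first event, or because a grade 2 cut was made between the two events.

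| Rule | Restart dose |
|---|---|
| One-capsule cut, Section 5.2 | 280 mg |
| Table 5-2, row two | 420 mg (no cut) |

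Difference: 420 − 280 = 140 mg/day. Ratio: 420/280 = 1.50. If the patient is on 560 mg at this point, text and table agree on 420 mg. The second conflict is therefore confined to patients on 420 mg at the time.

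**Step 4: search for a rule that settles it.** Section 5.2 also says to adjust for the worst toxicity seen, which concerns grade and not the restart dose after an earlier cut. Section 5.4 points to Table 5-2 in a parenthesis. Sections 1.3.3.3, 1.3.3.5 and 2.1 point to Section 5.2 as a whole. Sections 5.2.1, 5.3 and 5.5 deal with liver impairment, concomitant drugs and procedures. None of them gives an order of precedence.

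**The case against.** The strongest reply is that Section 5.2 largely answers the question already. The ban is categorical (*may not*), the restart sentence says *should*, and the table is only *recommended*. Read together, 560 mg is the default for patients still on 560 mg, and the ban caps everyone else. At the second event the text is likewise an instruction and the table a recommendation, so 280 mg is the better reading. This stands as the likelier intent and lowers the weight of the point. It remains an inference, because a specific restart rule can equally be read as an exception to a general ban.

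A second reply is to count the grade 2 episode as the first occurrence in Table 5-2, so that the next event falls in row two. That removes the table conflict at the first severe event. But the table directly follows the severe-event rules and is introduced as applying to those toxicities, and the restart sentence would still give 560 mg.

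Stronger readings are also tempting. A reader might infer from Section 5.4 that the table governs alone, so that the protocol in effect orders re-escalation. The documents do not support that: the reference is a parenthesis in a list of reasons for removal, and other sections send the reader to the whole of Section 5.2, ban included. A reader might also infer that a grade 2 cut uses up one of the two permitted reductions. That phrase follows two reductions described for severe events, and either reading is possible.

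**Conclusion.** The inconsistency is real and narrow. For a patient already at 420 mg because of grade 2 toxicity, the protocol gives 560 mg and at most 420 mg for the same restart (140 mg/day, 1.33-fold). For a patient on 420 mg at a second event it gives 420 mg and 280 mg (140 mg/day, 1.5-fold). The ban probably should prevail, but this is not stated.

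The conclusion assumes that one level means 140 mg and that the second event is a recurrence in the sense of Section 5.2. It requires both an optional grade 2 cut and a qualifying severe event. The documents give no frequency for that combination, so no number of affected patients can be offered.

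It is a minor dosing-safety matter, worth correcting because the correction is nearly free. A reader might infer that it weakens the trial's efficacy test. It does not: the response-rate hypotheses, the cohort sizes of 30 and 21, the power and the type I error are unchanged.

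**What to change.** Three small edits:

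1. To the end of the restart sentence in Section 5.2, add: *or at the current toxicity-reduced dose if that is lower*.
2. To row one of Table 5-2, add: *or at the current toxicity-reduced dose if lower*.
3. To row two, add: *or at 280 mg daily if the dose had already been reduced to 420 mg for toxicity*.

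A patient with no earlier cut keeps the present sequence of 560, 420, 280 mg, then stop. A patient cut to 420 mg before the first event restarts at 420 mg and then, at the second event, at 280 mg.

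Separately, ask the sponsor to state whether a grade 2 reduction counts towards the two reductions before discontinuation. That is a clinical choice which the documents leave open. It decides whether the patient just described stops at the third event or falls under row three. Sections 5.2.1 and 5.3 need no change for this point.

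The cost is one clause, two table rows and one answer from the sponsor. Sample size, visits and analysis are unaffected.
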